9.4.6 ANALYSIS OF THE SECONDARY EFFICACY ENDPOINTS

Following are the secondary efficacy endpoints:

- Percent change from Baseline in IASI total score at Week 16
- Proportion of subjects achieving IASI50 at Week 16
- Change and percent change from Baseline in IASI-E and IASI-S subscores at Week 16

9.4.6.1 CATEGORICAL ENDPOINTS

Frequency and percentages for each response Yes/No for categorical endpoints related to IASI will be presented separately by visit for both treatment arms. Subjects with missing scores at a given visit will be considered to have not met the criteria of interest (ie, nonresponse). Estimates of the difference between treatments (ANB019 – placebo) will be presented along with exact 95% CIs. Treatment arms will be compared using an exact test, as described in the SAP.

9.4.6.2 CONTINUOUS ENDPOINTS

Summary statistics will be provided for absolute scores of IASI, IASI-E, and IASI-S, as well as for change from Baseline by visit and treatment arm. A by-subject listing will be presented for each assessment, by visit.

Summary statistics will be provided for TEWL scores as well as for change from Baseline by visit and treatment arm.

Analyses involving endpoints of percent change will be implemented descriptively.

DocuSign Envelope ID: E4BE9C16-DB1E-4354-B874-2109B7254DAA

Efficacy and Safety of ANB019 in Subjects with Ichthyosis
Protocol ANB019-206

Version 1.0
30 October 2020

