3.2 SECONDARY OBJECTIVES AND ENDPOINTS

Secondary Objectives	Secondary Endpoints

To evaluate the effect of ANB019 compared with placebo on ichthyosis signs and symptoms, and quality of life in subjects with ichthyosis	
Percent change from Baseline in IASI total score at Week 16Proportion of subjects achieving IASI50 at Week 16Change and percent change from Baseline in IASI-E and IASI-S subscores at Week 16

To determine the safety of ANB019 in the treatment of ichthyosis	
Incidence of AEs, SAEs, and AEs leading to withdrawals, as well as changes in vital signs, clinical laboratory parameters (hematology, biochemistry, and urinalysis), and 12-lead ECGs

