9.4 STATISTICAL ANALYSES

9.4.1 GENERAL APPROACH

The statistical analysis will be performed using statistical analysis system (SAS[®]) Version 9.4 or higher. All details regarding the statistical analysis and the preparation of tables, listings, and figures will be described in the Statistical Analysis Plan (SAP) and approved by the Sponsor before database lock and any analysis is undertaken.

The default summary statistics for continuous variables include number of contributing observations, mean, SD, median, minimum, and maximum. For PK parameters, coefficient of variation (CV) and geometric mean will also be presented, as appropriate.

For categorical variables, the number and percentage (percentage of subjects in each category relative to the total number of subjects in the relevant analysis set or relative to the total number of subjects in the relevant analysis set with assessments available [where appropriate]) in each category will be the default summary presentation.

Unless otherwise specified, "Baseline" is defined as the last observed value of the parameter of interest prior to the first intake of study treatment (this includes unscheduled visits). For numerical variables, change from Baseline will be calculated as the difference between the value of interest and the corresponding Baseline value.

Unless otherwise specified, all formal statistical tests will be 2-sided at the 5% significance level. Point estimates of treatment differences will be accompanied with 2-sided 95% confidence intervals (CIs), where applicable.

In the case of normality assumption violations, appropriate nonparametric methods may be used for analysis.

All data will be presented in by-subject listings.

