9.4.5 ANALYSIS OF THE PRIMARY EFFICACY ENDPOINT

The primary efficacy endpoint is the change from Baseline in IASI total score at Week 16.

A general linear mixed model repeated measures (MMRM) analysis will be used to estimate the least-squares means (LSM) and associated standard errors for the change from Baseline in IASI total score to Week 16. The model will include change from Baseline in IASI total score at Week 16 as the dependent variable, fixed effects for treatment arm, categorical time point, and the treatment by time point interaction, and the Baseline IASI total score as a covariate. An appropriate covariance structure will be described in the SAP prior to database lock. Should the initial model not converge, alternate covariance structures or inclusion of fewer postBaseline visits (eg, Week 8 and Week 16 only) will be considered. Full details will be described in the SAP. The difference between LSMs (ANB019 – placebo) at Week 16 will be presented along with the associated 95% CI and p-value.

Possible effect of any other covariates as well as investigation of variables through sub-group analysis may also be investigated. Details of such analyses will be described in the SAP. Details of specific alternative statistical methods will be documented in the SAP.

In addition, descriptive statistics (n, mean, SD, median, minimum, and maximum) will be presented by visit.

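### Protocol 9.4.6.2 plans only by-arm summaries for Week 16 change in IASI-E and IASI-S, so a secondary objective worded against placebo has no pre-specified, baseline-adjusted estimate for erythema or scaling

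*Protocol*

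**What the plan says.** Protocol 3.2 words the secondary efficacy objective as a comparison: "To evaluate the effect of ANB019 compared with placebo on ichthyosis signs and symptoms". Among the endpoints under it, repeated in Section 9.4.6, is "Change and percent change from Baseline in IASI-E and IASI-S subscores at Week 16".

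The planned methods differ by endpoint:

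- **Primary, IASI total (9.4.5):** an MMRM with treatment, visit and their interaction, "and the Baseline IASI total score as a covariate". The difference in least-squares means "at Week 16 will be presented along with the associated 95% CI and p-value".
- **IASI50 (9.4.6.1):** missing counts as non-response. The between-arm difference "will be presented along with exact 95% CIs", with an exact test.
- **IASI-E and IASI-S change (9.4.6.2):** "Summary statistics will be provided for absolute scores of IASI, IASI-E, and IASI-S, as well as for change from Baseline by visit and treatment arm", plus listings.
- **Percent change (9.4.6.2):** "Analyses involving endpoints of percent change will be implemented descriptively".

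Section 9.4.7 carries the 9.4.6.2 method to the continuous exploratory endpoints.

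Two general statements also bear on this. Section 9.4.1 says: "Point estimates of treatment differences will be accompanied with 2-sided 95% confidence intervals (CIs), where applicable". Section 9.1 labels any secondary testing exploratory.

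The SAP of 12 January 2022 (Sections 1 and 7.3) performs no efficacy analysis because the study was terminated for low enrolment. It only lists the IASI scores.

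**The concern.** Summaries by arm do not in themselves deliver a comparison with placebo. The two subscores add up to the primary score (Protocol Appendix 8). The total gets a modelled difference with a CI, and so in unadjusted form does the responder endpoint built on it, but its two components get neither.

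Which component moves is a substantive question here. Protocol 2.1 hopes for less inflammation and, more tentatively, less scaling. Baseline erythema severity is also the only stratification factor (Section 6.3).

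The separate sentence that makes percent change descriptive suggests that absolute change may have been meant to receive more, but that is an inference.

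At stake are three things: a named estimate fixed in advance, use of each subject's own baseline subscore, and a stated way to handle subjects without a Week 16 score. Section 9.2 plans for three such subjects (16 to 14 and 8 to 7).

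**Working it through.** **Inputs from Protocol 9.2 (same in SAP 3.4), all for IASI total:** 14 versus 7 evaluable subjects, SD 9, baseline-to-Week-16 correlation r = 0.5, difference 12.3, two-sided alpha 0.05. Each subscore runs from 0 to 24 (Appendix 8).

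**Assumed, because the documents give no subscore figures:** r = 0.5 with a range of 0.3 to 0.7, and subscore SD 4.5 to 6.5. The SD range comes from two equal-SD subscores with correlation ρ that add to a total with SD 9: 2s²(1+ρ) = 81 gives s = 4.5 at ρ = 1 and s = 6.4 at ρ = 0. I use 6.5 as the upper value.

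**1. The plan's own figure.** SD of change = 9 × √(2(1−0.5)) = 9.0. SE = 9 × √(1/14 + 1/7) = 4.17. The noncentral t distribution with 19 df gives power 0.7997. The stated 80% is reproduced to rounding; exactly 80% needs a difference of 12.305. No figure is stated for the subscores.

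**2. 95% half-width in units of the score SD**, with √(1/14 + 1/7) = 0.463:

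- Unadjusted change: 2.093 × √(2(1−r)) × 0.463 (19 df)
- Baseline-adjusted: 2.101 × √(1−r²) × 0.463 (18 df)

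**3. Allowance for chance baseline imbalance.** With 21 subjects and one normal covariate, the variance of the adjusted difference is inflated on average by 1 + 1/17. The SE therefore rises by √1.0588 = 1.029. At r = 0.5 this gives 0.842 × 1.029 = 0.867, and 0.867/0.969 = 0.894.

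| r | Unadjusted | Adjusted | Narrower | Narrower after allowance |
|---|---|---|---|---|
| 0.3 | 1.146 | 0.928 | 19% | 17% |
| 0.5 | 0.969 | 0.842 | 13% | 10–11% |
| 0.7 | 0.750 | 0.695 | 7% | 5% |

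**4. In subscore points at r = 0.5.**

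- Unadjusted: 0.969 × 4.5 = 4.4 to 0.969 × 6.5 = 6.3
- Adjusted: 0.842 × 4.5 = 3.8 to 0.842 × 6.5 = 5.5
- Adjusted after the allowance: 0.867 × 4.5 = 3.9 to 0.867 × 6.5 = 5.6

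**5. Chance imbalance.** A one-SE baseline difference between arms is 0.463 SD. At r = 0.5 it moves the unadjusted change difference by (1 − 0.5) × 0.463 = 0.23 SD. Adjustment removes that shift.

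These are single-covariate calculations on subjects with Week 16 data. An MMRM would also use the earlier visits of subjects who drop out; I have not quantified that.

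**The case against.** The strongest reply is that the estimate is not out of reach. Section 9.4.1 makes n, mean and SD the default summaries, and 9.4.6.2 gives them for change by visit and arm. From these anyone can compute an unadjusted difference with a t-based CI. A reader might infer that the trial could not size the effect on erythema or scaling at all. The documents do not support that.

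The protocol also left room for more. Section 9.4.1 defers detail to the SAP and attaches CIs to treatment differences where applicable, and Section 9.1 anticipates secondary testing. This stands as permission, but neither sentence supplies a subscore estimate.

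Section 4.3 calls this a pilot study, and with 14 versus 7 subjects it is defensible to model the total and describe its parts. That stands against any claim from power. It does not explain why IASI50, in the same small sample, gets a difference and a CI.

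Three further readings go beyond the text:

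- That the subscores are analysed on observed cases only. Section 9.4.6.2 is silent on missing continuous scores; it states no such rule.
- That the rationale expects the drug to act first on inflammation. Section 2.1 gives no order. It is only more tentative about scaling.
- That the loss is 8.7 versus 7.6 points (the half-widths at SD 9). Those are on the total-score scale, where the MMRM is already planned, and they omit the small-sample allowance.

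Finally, the SAP drops the primary model as well. For the trial as run, the missing estimate follows from termination.

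**Conclusion.** The gap is real but modest, and it lies in the protocol as a design document. Two secondary endpoints that serve a comparative objective have no pre-specified difference, CI, baseline adjustment or missing-data rule, while their neighbours have at least a difference with a CI. What is lost is the pre-specified adjusted estimate.

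In precision, the loss is about 10–11% of CI width at r = 0.5 and about 5% at r = 0.7. With a subscore SD of 4.5 to 6.5, it is roughly 0.5 to 0.7 points of half-width on a 24-point scale (4.4 to 3.9, and 6.3 to 5.6). Correlation and SD are borrowed or assumed. Even the adjusted estimate would be imprecise, so the case rests on answering the stated objective in the same way as the primary.

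A reader might infer that correcting 9.4.6.2 would alter what this trial reports. It would not: SAP 7.3 provides listings only.

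**What to change.** In Protocol 9.4.6.2, and in any SAP that reinstates efficacy analysis, fit the Section 9.4.5 MMRM to change in IASI-E and in IASI-S. Use each subscore's own baseline as covariate and the same fallback if the model does not converge. Report the Week 16 difference in least-squares means with its 95% CI, labelled exploratory as Section 9.1 provides. State how missing scores are handled, and keep the descriptive tables.

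Because Section 9.4.7 mirrors 9.4.6.2, say explicitly whether the continuous exploratory endpoints follow the model or stay descriptive.

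The change needs no extra subjects, visits or alpha, because both subscores come from the IASI assessments already scheduled. It is not a re-run of planned output: the current SAP specifies no MMRM and has no efficacy table shells. If efficacy analysis is reinstated, the primary model must be programmed anyway, and two further outcomes add little. For the terminated trial no action is needed.

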9.4.7 ANALYSIS OF THE EXPLORATORY EFFICACY ENDPOINTS

Following are the exploratory efficacy endpoints:

- Change and percent change from Baseline in IASI total score at Weeks 1, 4, 8 and 12
- Proportion of subjects achieving IASI50 at Weeks 1, 4, 8, and 12
- Proportion of subjects achieving IASI75 at Weeks 1, 4, 8, 12, and 16
- Change and percent change from Baseline in IASI-E and IASI-S subscores at Weeks 1, 4, 8, and 12
- Change and percent change from Baseline in NASA at Weeks 1, 4, 8, 12, and 16 (for subjects with Netherton Syndrome only)
- Proportion of subjects achieving NASA50 at Weeks 1, 4, 8, 12, and 16 (for subjects with Netherton Syndrome only)
- Change and percent change from Baseline in IGA at Weeks 1, 4, 8, 12, and 16
- Proportion of subjects achieving an IGA of clear (0) or almost clear (1) at Weeks 1, 4, 8, 12, and 16
- Proportion of subjects with at least 2-point decrease in IGA at Weeks 1, 4, 8, 12, and 16
- Change and percent change from Baseline in worst and average pruritus NRS at Weeks 1, 4, 8, 12, and 16
- Change and percent change from Baseline in worst and average pain NRS at Weeks 1, 4, 8, 12, and 16
- Proportion of subjects with at least 3-point decrease in worst pruritus NRS at Weeks 1, 4, 8, 12, and 16 for subjects with a Baseline worst pruritus NRS of at least 3
- Proportion of subjects with at least 4-point decrease in worst pruritus NRS at Weeks 1, 4, 8, 12, and 16 for subjects with a Baseline worst pruritus NRS of at least 4
- Proportion of subjects with at least 3-point decrease in worst pain NRS at Weeks 1, 4, 8, 12, and 16 for subjects with a Baseline worst pain NRS of at least 3
- Proportion of subjects with at least 4-point decrease in worst pain NRS at Weeks 1, 4, 8, 12, and 16 for subjects with a Baseline worst pain NRS of at least 4
- Change from Baseline in BSA at Weeks 1, 4, 8, 12, and 16
- Change from Baseline in DLQI and CDLQI scores at Weeks 1, 4, 8, 12, and 16
- Proportion of subjects in each response category for the PGI-S and PGI-C at Weeks 1, 4, 8, 12, and 16
- Change from Baseline in iQoL-32 score at Weeks 4, 8, 12, and 16
- Change from Baseline in TEWL at Weeks 4, 8, 12, and 16
- Proportion of subjects receiving rescue medication at Weeks 4, 8, 12, and 16
- Proportion of subjects achieving IASI50 from Week 20 through Week 40
- Proportion of subjects achieving IASI75 from Week 20 through Week 40
- Change and percent change from Baseline in IASI total score from Week 20 through Week 40
- Change and percent change from Baseline in IASI-E and IASI-S subscores from Week 20 through Week 40

DocuSign Envelope ID: E4BE9C16-DB1E-4354-B874-2109B7254DAA

Efficacy and Safety of ANB019 in Subjects with Ichthyosis
Protocol ANB019-206

Version 1.0
30 October 2020

- Change and percent change from Baseline in NASA from Week 20 through Week 40 (for subjects with Netherton Syndrome only)
- Proportion of subjects achieving NASA50 from Week 20 through Week 40 (for subjects with Netherton Syndrome only)
- Change and percent change from Baseline in IGA from Week 20 through Week 40
- Proportion of subjects achieving an IGA of clear (0) or almost clear (1) from Week 20 through Week 40
- Proportion of subjects with at least 2-point decrease in IGA from Week 20 through Week 40
- Change and percent change from Baseline in worst and average pruritus NRS from Week 20 through Week 40
- Proportion of subjects with at least 3-point decrease in worst pruritus NRS from Week 20 through Week 40 for subjects with a Baseline worst pruritus NRS of at least 3
- Proportion of subjects with at least 4-point decrease in worst pruritus NRS from Week 20 through Week 40 for subjects with a Baseline worst pruritus NRS of at least 4
- Change and percent change from Baseline in worst and average pain NRS from Week 20 through Week 40
- Proportion of subjects with at least 3-point decrease in worst pain NRS from Week 20 through Week 40 for subjects with a Baseline worst pain NRS of at least 3
- Proportion of subjects with at least 4-point decrease in worst pain NRS from Week 20 through Week 40 for subjects with a Baseline worst pain NRS of at least 4
- Change from Baseline in BSA from Week 20 through Week 40
- Change from Baseline in iQoL-32 score from Week 20 through Week 40
- Change from Baseline in DLQI and CDLQI scores from Week 20 through Week 40
- Proportion of subjects in each response category for the PGI-S and PGI-C from Week 20 through Week 40
- Change from Baseline in TEWL from Week 20 through Week 40
- Proportion of subjects receiving rescue medication from Week 20 through Week 40

Methods for analyzing the above categorical and continuous efficacy endpoints will mirror the methods described in [Section 9.4.6.1](#) and [9.4.6.2](#), respectively.

9.4.8 SAFETY ANALYSES

Following are the primary safety and tolerability endpoints:

- Assessment of AEs, SAEs, and AEs leading to withdrawal.
- Vital signs.
- 12-Lead ECG.
- Clinical safety laboratory tests (hematology, biochemistry, and urinalysis).

All safety analyses will be performed on the safety analysis set.

DocuSign Envelope ID: E4BE9C16-DB1E-4354-B874-2109B7254DAA

Efficacy and Safety of ANB019 in Subjects with Ichthyosis
Protocol ANB019-206

Version 1.0
30 October 2020

9.4.8.1 ADVERSE EVENTS AND SERIOUS ADVERSE EVENTS

A TEAE is defined as:

- A new event that occurs during or after first dose of study treatment or,
- Any event present at Baseline that worsens in either intensity or frequency after first dose of study treatment.

Adverse events will be coded using the MedDRA and only TEAEs will be summarized. Number of events and percentage will be tabulated by preferred term (PT) and system organ class (SOC). Multiple occurrences of an AE for a subject will only be counted once per SOC and PT. Percentages will be determined relative to the subjects in the safety analysis set for the given treatment arm.

If the intensity or seriousness of the AE changes, the overall intensity or seriousness will be the maximum intensity or seriousness of the multiple occurrences. The TEAEs, SAEs, TEAEs leading to treatment discontinuation, and TEAEs leading to withdrawal of subject will be tabulated for each treatment arm.

All AE data will be listed for each subject.

Summaries over SOC and PT of TEAEs, TEAEs leading to death, SAEs, and TEAEs that led to discontinuation from the study or study treatment will be presented by treatment. Summaries will also be presented by relatedness to the study treatment and the severity of the TEAE.

9.4.8.2 12-LEAD ELECTROCARDIOGRAM, VITAL SIGNS, AND CLINICAL SAFETY LABORATORY TESTS

Summaries and listings of data for vital signs and safety laboratory tests result (hematology, biochemistry, and urinalysis) will be presented. Appropriate descriptive statistics will be summarized for the observed value at each scheduled assessment and for the corresponding change from Baseline.

For hematology and biochemistry tests, listings of subject data will also flag up any abnormal or out-of-range values. Clinically significant changes in the laboratory test parameters will be summarized and listed. Hematology and biochemistry data will be reported in System International units.

Descriptive statistics will be used to present the safety outcomes including, weight, BMI, 12-Lead ECG, vital signs, and clinical laboratory test results.

Change from Baseline will also be summarized for vital signs, and clinical laboratory tests results.

All ECG data results (normal/abnormal) will be summarized using frequency and percentage, and parameter values will be summarized descriptively. Clinically significant abnormalities will be presented in by-subject listings.

9.4.9 PHARMACOKINETIC ANALYSES

Limited ANB019 PK parameter analysis will be evaluated by assessment of drug concentrations in serum. These drug concentrations will be listed and summarized for each sampling time point using appropriate descriptive statistics. The PK parameters will be summarized using appropriate descriptive statistics.

9.4.9.1 DERIVATION OF PHARMACOKINETIC PARAMETERS

Where possible, PK parameters will be derived using noncompartmental methods. The actual sampling times will be used in the PK parameter calculations. Further details of PK analysis, data handling, analysis procedures, and data reporting will be detailed in a separate analysis plan.

DocuSign Envelope ID: E4BE9C16-DB1E-4354-B874-2109B7254DAA

Efficacy and Safety of ANB019 in Subjects with Ichthyosis
Protocol ANB019-206

Version 1.0
30 October 2020

9.4.9.2 PHARMACOKINETIC CONCENTRATION DATA ANALYSIS

A subject listing of all concentration-time data following SC injections will be presented by subject and scheduled sample collection time.

Concentration data of ANB019 will be summarized by day and nominal time point using the number of observations, arithmetic mean, SD, CV, minimum, median, maximum, and geometric mean.

Graphs for mean concentration-time data following SC administration will be presented. Individual subject concentration-time plots will also be presented.

Mean trough concentrations-time data will be graphically displayed for samples collected at the visits specified in the SoA (see [Section 1.3](#)) to visually assess time to attainment of steady state. Time to steady state may also be explored by using inferential statistics, if deemed appropriate. Other presentations of data may be added at the discretion of the PK scientist, as appropriate, and will be described in detail in a separate analysis plan.

9.4.9.3 PHARMACOKINETIC PARAMETER DATA ANALYSIS

Where possible, PK parameters will be summarized using number of observations, arithmetic mean, SD, CV, minimum, median, maximum, geometric mean, and geometric CV, with the exception of time to maximum observed concentration (T_{max}), which should be reported with n, minimum, median, and maximum only.

Graphs of parameters may be added at the discretion of the PK scientist, as appropriate, and will be described in detail in a separate analysis plan.

9.4.9.4 POPULATION PHARMACOKINETICS ANALYSIS

Pharmacokinetic data from the study may also be used for population PK and PK/response analyses. If done, a separate analysis plan will be prepared, and results will be reported separately from the Clinical Study Report (CSR).

9.4.10 IMMUNOGENICITY ANALYSES

Observed values for ADA levels/status will be listed by-subject and summarized with descriptive statistics based on the safety analysis set. If data permits, correlation will be analyzed between ADA levels, serum concentration, and safety and efficacy endpoints.

Frequency and percentage of ADA response will be presented and listed and correlated to safety and PK endpoints.

